2.2.4 Analysis visits

All assessments, including unscheduled assessments, will be allocated to analysis windows. Tables and listings will present the analysis windows as defined below, not the CRF visits. Assessments will be allocated using their relative day in the phase (see section 2.2.3).

Table 4: Analysis visits

Phase	Analysis window	Target ADY	Lower limit ADY	Upper limit ADY
Screening	Screening ^d	-14	-INF	1
Treatment	Baseline ^d	1	-INF	1 ^e
	Week 1	8	1 ^e	11
	Week 2	15	12	18
	Week 3	22	19	25
	Week 4	29	26	32
	Week (4 + x ^a)	29 + (x ^a *7 days)	26 + (x ^a *7 days)	32 + (x ^a *7 days)

	Week 23	162	159	165
Week 24	169	166	n ^b	
Follow-up	SEFU Week 4	28	1	42
	SEFU Week 8	56	43	n ^c

^a x=1,...,18; ^bRelative day of End-of-Treatment phase; ^cRelative day of end of follow-up phase

^d As the interval of screening and baseline are overlapping, the same assessment can be attributed to both timepoints.

^e An assessment on day 1 will be attributed to baseline in case it is before the injection, to Week 1 otherwise, unless the assessment is related to questionnaires for which time will not be considered and therefore be allocated to baseline.

Table 5: Analysis visits for total IgG and PK

Phase	Analysis window	Target ADY	Lower limit ADY	Upper limit ADY
Treatment	Baseline	1	-INF	1 ^a
	Week 1	8	1 ^a	11
	Week 2	15	12	18
	Week 3	22	19	29
	Week (3 + x ^b *2)	22 + (x ^b *14)	16 + (x ^b *14)	29 + (x ^b *14)
	Week 23	162	156	165
	Week 24	169	166	n ^c
Follow-up	SEFU Week 4	28	1	42
	SEFU Week 8	56	43	n ^d

^a An assessment on day 1 will be attributed to baseline in case it is before the injection to Week 1 otherwise. In addition, baseline pre and post dose PK assessments will be attributed to the baseline.

^b x ranges from 1 to 9.

^c relative day of end of treatment phase

^d relative day of end of FU phase

	Statistical Analysis Plan	
ARGX-113-2004	Final analysis	Final 1.0 of 7NOV2023

Table 6: Analysis visits for anti-platelet antibodies

Phase	Analysis window	Target ADY	Lower limit ADY	Upper limit ADY
Treatment	Baseline	1	-INF	1 ^a
	Week 7	50	1 ^a	78
	Week 15	106	79	134
	Week 23	162	135	165
	Week 24	169	166	n ^b

^a An assessment on day 1 will be attributed to baseline in case it is before the injection to Week 7 otherwise.

^b relative day of end of treatment phase

Table 7: Analysis visits for immunogenicity

Phase	Analysis window	Target ADY	Lower limit ADY	Upper limit ADY
Screening	Screening ^a	-14	-INF	1
Treatment	Baseline	1	-INF	1 ^b
	Week 3	22	1	36
	Week (3 + x ^c *4)	22 + (x ^c *28)	9 + (x ^c *28)	36 + (x ^c *28)
	Week 23	162	149	165
	Week 24	169	166	n ^d
Follow-up	SEFU Week 4	28	1	42
	SEFU Week 8	56	43	n ^e

^a As the interval of screening and baseline are overlapping, it may be that the same assessment will be attributed to both timepoints.

^b An assessment on day 1 will be attributed to baseline in case it is before the injection to Week 3 otherwise.

^c x ranges from 1 to 4.

^d relative day of end of treatment phase

^e relative day of end of FU phase

Baseline is defined in section 2.2.2.

Per parameter and analysis window, the value closest to the target ADY will be used in analysis tables, other values will only be listed. If more than 1 value is located at the same distance from the target, then the value latest in time will be selected. The value latest in time will be identified using, in order of preference, the assessment time, the visit label, or the group identifier. Missing values are removed before the selection is made.

For efficacy only: In case of (partially) missing date/time fields, the CRF visit label will be used to allocate to the correct analysis visit (VISIT2 becomes Week 1, VISIT3 becomes Week 2 etc.). For VISIT = END_OF_STUDY_EARLY_DISCONTINUATION the corresponding analysis visit from ADSV should be used.

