Visit																																																	
Trial day	-14 to -1	1	8	15	22	29	36	43	50	57	64	71	78	85	92	99	106	113	120	127	134	141	148	155	162	169																							
Visit window, days																																																	
Pharmacokinetics ^{h,n}		X	X	X	X	X ^o	X ^o	X ^o	X ^o	X ^o	X ^o	X ^o	X ^o	X ^o	X ^o	X ^o	X ^o	X ^o	X ^o	X ^o	X ^o	X ^o	X ^o	X ^p	X	X	X	X	X	X																			
Randomization ^f		X																																															
IMP administration ^s		X	X	X	X	----- qw or q2w administration -----																																											
Caregiver informed consent form ^t																										X																							
IMP (self-)administration training ^{s,u}																										X																							
Collecting information related to hospitalization for ITP management		----- X -----																																															
Concomitant therapies/procedures ^v		----- X -----																																															
Adverse events ^v		----- X -----																																															

FACT-Fatigue=Functional Assessment of Chronic Illness Therapy-Fatigue; FACT-Th6=Functional Assessment of Cancer Therapy-Th6; IMP=investigational medicinal product; ITP=immune thrombocytopenia; ITP-PAQ=ITP-Patient Assessment Questionnaire; qw=weekly; q2w=every other week; SF-36 (v2)=Short Form 36 (version 2); WHO=World Health Organization

^a **Trial Period:**

Screening Period: maximum 14 days

Treatment Period: Weekly subcutaneous (SC) IMP administrations for visit 1 up to and including visit 4. As of visits 5 to 16, a qw or q2w IMP administration schedule will be followed. From visits 17 to 24, participants will be fixed on the dose schedule they were receiving at visit 16 or at the last visit at which IMP was administered (ie, either qw or q2w). There is a permissible visit window of +2 days during the treatment phase as well as the follow-up period. Every effort should be made to schedule every visit on the exact day (which is relative to baseline randomization [visit 1]).

The frequency (ie, qw or q2w) of IMP administrations depends on predefined criteria set forward in Section 6.5 of the protocol.

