^k At the screening visit, the total IgG level must be determined by the central laboratory (exclusion criterion 9).

^l Only for women of non-childbearing potential.

^m To maintain the blind, the IgG testing cannot be performed locally.

ⁿ To be collected predose, on the day of IMP administration.

^o If the visit does not coincide with an IMP administration, then the assessment should be performed at the next IMP visit.

^p If the visit does not coincide with an IMP administration, then the assessment should **NOT** be performed.

[REDACTED].
^r Randomization to be completed before administration of IMP.

^s Participants or their caregivers will be invited to receive training to (self-)administer the IMP while under supervision at least 4 times in the last 10 weeks, until they are capable of and comfortable with the (self-)administration ([self-]administration without supervision is foreseen only in the open-label extension trial ARGX-113-2005, not in ARGX-113-2004).

^t To be obtained before initiation of the IMP administration training.

^u The IMP (efgartigimod PH20 SC or placebo PH20 SC) will be administered as an SC injection at each IMP administration visit. Participants will remain at the trial site for at least 30 minutes following the end of the injection for routine safety monitoring based on the participant's clinical status. Assessment of the dosing regimen as described in Section 6.5 will be applied.

^v Adverse events, procedures, and intake of concomitant medication(s) will be monitored continuously from signing the ICF until the last trial-related activity, unless the participant withdraws consent. In case of early discontinuation, any adverse events/serious adverse events should be assessed until the participant has ended the trial or until satisfactory resolution or stabilization. All available vaccination history will be recorded as part of the participant's prior medication for vaccinations received in the past, or concomitant medication for vaccinations received during the trial.

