 - ^h Laboratory assessments include all parameters mentioned in Section 10.2. On days that IMP is administered, samples for laboratory assessments should be collected before dosing, unless otherwise requested.
 - ⁱ At the screening visit, if the investigator detects 1 or more screening laboratory abnormalities which are not aligned with the medical history and clinical evaluation of the participant, the result(s) should be confirmed if still within the screening window. For rescreening criteria see Section 5.4.
 - ^j Only for women of childbearing potential.
 - ^k At the screening visit, the total IgG level must be determined by the central laboratory (exclusion criterion 9).
 - ^l Only for women of non-childbearing potential.
 - ^m To maintain the blind, the IgG testing cannot be performed locally.
 - ⁿ To be collected predose, on the day of IMP administration.
 - ^o If the visit does not coincide with an IMP administration, then the assessment should be performed at the next IMP visit.
 - ^p If the visit does not coincide with an IMP administration, then the assessment should **NOT** be performed.
 - ^q Only in investigative sites participating in the platelet functionality substudy. To be collected as the last sample predose.
 - ^r Randomization to be completed before administration of IMP.
 - ^s Participants or their caregivers will be invited to receive training to (self-)administer the IMP while under supervision at least 4 times in the last 10 weeks, until they are capable of and comfortable with the (self-)administration ([self-]administration without supervision is foreseen only in the open-label extension trial ARGX-113-2005, not in ARGX-113-2004).
 - ^t To be obtained before initiation of the IMP administration training.
 - ^u The IMP (efgartigimod PH20 SC or placebo PH20 SC) will be administered as an SC injection at each IMP administration visit. Participants will remain at the trial site for at least 30 minutes following the end of the injection for routine safety monitoring based on the participant's clinical status. Assessment of the dosing regimen as described in Section 6.5 will be applied.

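### SAP Table 5 windows for total IgG and PK close 7 days after target, so a deferred sample taken 1 or 2 days late moves to the next week and can push a valid value out of the by-visit tables

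*SAP*

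**What the plan says.** SAP 2.2.4 ("Table 5: Analysis visits for total IgG and PK") gives Week 3+2x a target of day 22+14x and limits of 16+14x to 29+14x, where "x ranges from 1 to 9". Week 3 runs from day 19 to 29 and Week 23 from day 156 to 165. Assignment is by relative day: "Tables and listings will present the analysis windows as defined below, not the CRF visits". When a window holds more than one value, "Per parameter and analysis window, the value closest to the target ADY will be used in analysis tables, other values will only be listed".

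The Schedule of Activities (Protocol 1.3, repeated in SAP 9.5.1) requires PK and total IgG samples to be taken predose on a dosing day. Footnote o covers a sample due at a visit without dosing: "If the visit does not coincide with an IMP administration, then the assessment should be performed at the next IMP visit". At visit 24, footnote p applies instead: "If the visit does not coincide with an IMP administration, then the assessment should NOT be performed". On timing, footnote a of the schedule states: "There is a permissible visit window of +2 days during the treatment phase as well as the follow-up period". Visit days are counted from visit 1.

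The windows feed the by-visit trough and total IgG summaries, including those by fixed dosing regimen (SAP 4.2.3 and 4.3.3). SAP 2.2.4, 4.2 and 4.3 contain no rule for deferred samples. The visit-label fallback in 2.2.4 is for efficacy only, and only for missing or partial dates.

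**The concern.** The upper limit of target +7 holds a deferred sample only if the later visit takes place on its exact day. The protocol's own tolerance allows two more days, and on those days the sample belongs to the next window. A fully compliant sample can then be tabulated under a later week and displace the value that was due there.

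The participants chiefly exposed are those on every-other-week dosing whose doses fall on odd-numbered visits. Under Protocol 6.5 no dose is given at the visit that confirms the switch. If that visit is even, later doses fall on odd visits and every even-visit sample is deferred. A weekly participant whose dose is withheld at a sampling visit, for instance after IVIg rescue (Protocol 6.6.4), is deferred in the same way. Trough concentration and total IgG are named secondary endpoints, and the every-other-week rows of the by-regimen tables are where the effect concentrates.

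**Working it through.** **Inputs**
- Scheduled day of visit v: 1 + 7(v−1) (Protocol 1.3).
- Sampling visits subject to deferral: even visits 6 to 22. These are read from the schedule in Protocol 10.9, where the column layout is legible, and they agree with the SAP Table 5 targets for x = 1 to 9.
- Lateness δ = 0, 1 or 2 days.
- Window limits and the closest-to-target rule from SAP 2.2.4.

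**Step 1: reproduce the table.** Week 3+2x corresponds to visit 4+2x, whose day is 1 + 7(3+2x) = 22+14x, the stated target. Lower limit minus target: 16 − 22 = −6. Upper limit minus target: 29 − 22 = +7. The windows are contiguous. On-schedule samples (target +0 to +2) are always placed correctly.

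**Step 2: place the deferred samples.** A sample due at visit v and taken at visit v+1 falls on day 1 + 7v + δ, which is target + 7 + δ.

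| Due at | Own window | δ = 0 | δ = 1 | δ = 2 |
|---|---|---|---|---|
| Visit 6 (Week 5) | 30–43 | 43, Week 5 | 44, Week 7 | 45, Week 7 |
| Visit 8 (Week 7) | 44–57 | 57, Week 7 | 58, Week 9 | 59, Week 9 |
| Visit 22 (Week 21) | 142–155 | 155, Week 21 | 156, Week 23 | 157, Week 23 |

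All nine visits from 6 to 22 behave the same way.

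**Step 3: collisions.** Take visit 7 on day 44 and visit 9 on day 57. They are 13 days apart, which meets the 12-day minimum in Protocol 6.5. Both samples fall in Week 7 (target 50). Distances are 50 − 44 = 6 and 57 − 50 = 7, so the day 44 value is tabulated as Week 7, the day 57 value is only listed, and Week 5 is empty. In later pairs the earlier week is empty unless the sample before it was late as well.

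**Step 4: size.** In a run of n consecutive deferred samples ending at visit 22, a value is left out when one sample is late (probability p) and the next is exact (1−p). There are n−1 such pairs, so the share left out is p(1−p)(n−1)/n.
- n = 9, p = 10%: 0.09 × 8/9 = 8%
- n = 9, p = 20%: 0.16 × 8/9 = 14%
- n = 9, p = 50%: 0.25 × 8/9 = 22%
- n = 4 (visits 16, 18, 20 and 22), p = 20%: 0.16 × 3/4 = 12%

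A simulation with n = 9 agrees. At 20% late, 66% of samples were tabulated in their own week, 20% in the next week and 14% were listed only. At 40% late the split was 39%, 40% and 21%.

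The formula does not cover an isolated deferral, or a run that ends with a return to weekly dosing. There a late deferred sample meets an on-schedule sample 0 to 2 days from target and is itself the one only listed (day 44 against day 50, for example).

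**Step 5: the other windows.** Table 7 closes at target +14 (36+28x against 22+28x). Table 6 closes at target +28 for Weeks 7 and 15 (78 against 50, 134 against 106). Both absorb a deferral of 7 to 9 days, so the gap is specific to Table 5.

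**The case against.** The best defence is that −6 to +7 is simply the nearest-target partition for targets 14 days apart. Day 44 is 6 days from the Week 7 target and 8 from the Week 5 target, and the SAP says openly that it tabulates windows and not visits. On that view the label is a choice and not an error. This stands for the label taken alone. It does not answer the collisions, where one week is left empty and a compliant value leaves the tables.

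It is also true that a deferral on its exact day is already accommodated, that sites are asked to keep to exact days, and that every lateness rate above is assumed. Nine deferrals require a switch confirmed at visit 6 with no return to weekly dosing; most runs would be shorter. The absolute count may be small. Suppose, for illustration only, that every-other-week participants match the planned 21.8% response rate among (180 + 39) × 2/3 = 146 active participants, and that half are dosed on odd visits. That is about 32 and then 16 participants, so at 20% lateness and 12% to 14% left out, about 2 values per visit.

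A reader might infer more than the documents support:
- That all deferred samples are misplaced. Those at exactly +7 stay in their own week unless displaced.
- That data are lost. The values remain in the listings.
- That mean trough or IgG is biased. Displaced and retained values are both predose samples from the same participant, and no direction or size of bias follows from the windows.
- That only every-other-week participants are affected. A withheld weekly dose has the same effect.
- That efficacy is touched. Efficacy uses the Table 4 windows.

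**Conclusion.** The point holds as a windowing fault in descriptive tables. SAP Table 5 does not allow for the combination of the deferral rule and the 2-day visit tolerance, so compliant samples at target +8 or +9 move to the next week and can displace a compliant sample at +7. Among samples in a run of deferrals, roughly 8% to 22% would be left out for assumed late rates of 10% to 50% with nine deferrals, and about 12% for four deferrals at 20%. These figures assume independent lateness. Neither the late rate nor the share of participants dosed every other week on odd visits is given, so no trial-wide percentage can be stated. The effect stops at the by-visit trough and total IgG summaries, including those by fixed dosing regimen. No tested endpoint changes. It is worth correcting because the remedy is simple.

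**What to change.** Change four limits in SAP Table 5:

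| Window | Current | Proposed |
|---|---|---|
| Week 3 | 19–29 | 19–31 |
| Week 3+2x (x = 1 to 9) | 16+14x to 29+14x | 18+14x to 31+14x |
| Week 23 | 156–165 | 158–165 |

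The middle windows become target −4 to target +9. They stay contiguous: Week 3 ends on day 31 and Week 5 starts on 18 + 14 = 32; Week 21 ends on 31 + 126 = 157 and Week 23 starts on 158. On-schedule samples (target +0 to +2) and one-visit deferrals (target +7 to +9) then all fall in their intended week, and the simulation gave no misplacement and no omission under any delay pattern tried. Allocating PK and total IgG by scheduled visit would do the same.

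The cost is an edit to one table, with no new data and no change to the efficacy windows. The small downside is that a sample at +8 or +9 carries its scheduled week although it is nearer in days to the next target; a footnote can say so. Deferrals of more than one visit, such as prolonged withholding under Protocol 6.7, are not covered, and the SAP should state how they are assigned.

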2.2.5 Worst-case

A worst-case analysis visit will be created for parameters for which abnormalities and/or toxicity grades are defined to summarize values considered as the worst-case. For abnormalities it is derived per parameter and in case both the lowest and the highest values are considered abnormal, a participant can have 2 worst-case analysis

	Statistical Analysis Plan	
ARGX-113-2004	Final analysis	Final 1.0 of 7NOV2023

visits for a same parameter. For toxicity grades the worst-case is the value associated to the highest toxicity grade and is derived per parameter and toxicity direction (hypo /hyper).

All non-missing postbaseline values, including unscheduled assessments will be considered when deriving the worst-case analysis visit.

2.3 IMPUTATION AND ROUNDING RULES

2.3.1 *Missing values*

Missing values for safety will not be imputed (ie, observed cases analysis). For imputation on missing values related to efficacy, see appropriate section of the applicable efficacy endpoint.

2.3.2 *Values below or above a threshold*

Anti-drug antibodies (ADA) against efgartigimod: titer of positive ADA samples reported as ‘negative titer’ (see section 4.4.2.1) will be imputed by 1. Antibodies (Ab) against rHuPH20: positive rHuPH20 Ab samples reported as ‘negative titer’ (see section 4.4.2.2) will be imputed by 5. NAb against rHuPH20: positive rHuPH20 NAb samples reported as ‘negative titer’ (see section 4.4.2.4) will be imputed by 100. Listings will always present ‘negative titer’.

Safety values expressed as below (or above) the detection limit will be imputed by the value of the detection limit itself. Listings will always show the non-imputed values.

PK concentrations below the detection limit will be flagged as Below the lower Limit of Quantification (BLQ) in the listings. For descriptive statistics by scheduled timepoint, BLQ values will be set to zero. For Above the upper Limit of Quantification (ALQ) values, all ALQ values will be set to the upper limit of quantification for the descriptive statistics by scheduled timepoint. Listings will always present the original value.

Total IgG values expressed as below or above the limit of quantification (BLQ or ALQ, respectively) will be imputed by the value of the detection limit itself. For participants with a baseline total IgG value below/above the quantification limit, total IgG will be excluded from the statistical analyses involving change and percent change from baseline. Listings will always show the non-imputed values.

2.3.3 *Rounding*

Variables will be rounded to the appropriate number of decimals at display level:

- Time since diagnosis and BMI will be rounded to 1 decimal.
- Ratios will be rounded to the number of decimals of the parameter with the least number of decimals.
- PD and safety laboratory results will be rounded to a maximum of 3 decimals.

2.3.4 *Outliers*

There will be no outlier detection. All measured values will be included in the analyses.

	Statistical Analysis Plan	
ARGX-113-2004	Final analysis	Final 1.0 of 7NOV2023

2.4 PRESENTATION OF RESULTS

All descriptive outputs described in this SAP will be repeated by origin (Japanese / Non-Japanese / overall as defined in the study protocol) to support the summary document of the J-MAA submission. The definition of a Japanese participant in the protocol is a participant whose parents and 4 grandparents are Japanese, who has the Japanese nationality, was born in Japan, has not lived outside of Japan for a total of >10 years, and currently lives in Japan. Note that these additional outputs will not be included in the submissions to other health authorities.

To support the marketing authorization application in China, all descriptive outputs in this SAP, except PK and PD, will be repeated on the Mainland Chinese and East Asian subpopulations. PK and PD analyses will be repeated by origin (Mainland Chinese / Non-Mainland Chinese and East Asian / Non-East Asian). Mainland Chinese is defined as any participant enrolled by an investigational site located in mainland China and with a race “Asian”. East-Asian is defined as any participant enrolled by an investigational site located in East Asia and with a race “Asian”.

These additional descriptive outputs will not be included in the submissions to other health authorities.

2.4.1 *Calculation of descriptive statistics and percentages*

For continuous variables, full descriptive statistics will only be presented if there are at least 2 non-missing observations. Alternatively, only the number of non-missing data points and mean are shown.

Descriptive statistics will include the number of non-missing data points, the arithmetic mean, the standard deviation (SD), the median, minimum, Q1, Q3, and maximum. In addition, for PD, the standard error (SE) will be provided. For efficacy and descriptive tables by analysis visit, the standard error (SE) and 95% CI will be provided in addition.

Descriptive statistics for PK concentrations will include n (number of observed values), arithmetic mean, SD, median, minimum and maximum, coefficient of variation (CV%), geometric mean and geometric CV%.

Serum concentrations will be reported as received by the bioanalytical laboratory. Descriptive statistics will be presented with 3 significant digits in $\mu\text{g/mL}$ (where appropriate), except values ≥ 1000 which will be presented without the decimals and rounded to the nearest integer. If at least one BLQ value is reported at a specific time point, the GM and geometric CV% for that time point will not be calculated. In addition, if more than half of the values per time point are BLQ, the arithmetic mean will be reported as BLQ and SD, CV%, GM, and geometric CV% will not be calculated.

For event-type safety data, the number and percentage of participants with an event will be shown. The denominator will be the number of all participants in the analysis set per treatment and phase.

For frequency tabulations and cross-tabulations, the denominator will be the number of all participants in the analysis set per treatment. For tables where results are shown by analysis visit, the denominator will be the number of all participants in the analysis set per treatment and per analysis visit. Missing values will never be included in the

	Statistical Analysis Plan	
ARGX-113-2004	Final analysis	Final 1.0 of 7NOV2023

denominator count when computing percentages. For cross-tabulations of postbaseline results versus baseline results, a ‘missing’ category will be shown for baseline results if applicable.

